5.4 STUDY DRUG ACCOUNTABILITY

The initial study drug shipment will be shipped after all required regulatory documentation has been received by the manufacturer and a Clinical Trial Agreement fully executed.

The study drug will only be dispensed to patients who meet the eligibility criteria and are randomized to a treatment arm in the trial. An accurate and current accounting of the dispensing and return of study drug for each patient will be maintained on an ongoing basis by the Investigator or his/her designated personnel. The number of study drug dispensed and returned by the patient will be recorded on the Investigational Product Accountability Log. The study monitor will verify these documents throughout the course of the study.

The disposition of any unused study drug should be performed per institutional guidelines. The Investigator must ensure that all investigational product is destroyed in compliance with the applicable environmental regulations, institutional policy, and any other special instructions provided by the manufacturer. Drug destruction must be adequately documented.

5.5 MEASURES OF TREATMENT COMPLIANCE

At each clinic visit, patients will be asked to return any remaining study drug from the previous dosing cycle as well as all used and unused study drug containers.

The overall treatment compliance will be defined as the total dose in mg taken during the study divided by the expected total dose in mg. Patients completing their last cycle on capsules should continue with a maximum of 8 capsules per day and patients on tablets should have a maximum of 4 tablets per day.

Tablets that are not returned will be considered to have been taken, unless otherwise specified in the case report form (CRF).

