5.3.2 Packaging, Storage, and Labeling

The apalutamide 60-mg tablets will be packaged in 120-count, 160 cc high-density polyethylene (HDPE) bottles with child-resistant caps. Bottles will include desiccant.

Each bottle of study drug will be labeled with the required regulatory agency warning statement, the protocol number, the Sponsor's name, and directions for patient use and storage. The Investigator will ensure that the study drug is stored in appropriate conditions in a secure location with controlled access. For clinical formulation-specific and batch-specific storage instructions, see the packaging label.

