5.3.3 Drug Administration

Apalutamide tablets will be administered orally on a continuous daily dosing regimen at a dose of 240 mg per day (4 x 60-mg tablets) with or without food.

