5.3.4 Cycle Management

For the purposes of the study, a treatment cycle will consist of 4 weeks (28 days).

It is anticipated that individual patients may occasionally forget to take a dose. In those cases, missed doses should only be replaced if the patient remembers within a 12-hour window. After that, patients should just take the next dose the following day, without compensating for the missed dose (including vomited doses). In the event of dose delays due to transient toxicity, tumor assessments should remain on schedule independent of cycle length.

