7.1.3 Physical Examination

A complete physical examination will be performed by either the Investigator or a sub-Investigator at Screening. Qualified staff (e.g., nurse practitioner or physician assistant) may complete either a full or abbreviated physical exam at all other visits. New abnormal physical exam findings must be documented and followed by a physician or other qualified staff at the next scheduled visit. All physical exams may be performed over a telemedicine visit.

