12 STATISTICAL METHODS AND CONSIDERATIONS

12.1 ANALYSIS POPULATIONS

Safety Analysis Population [SAFETY]: All patients who receive at least one dose of study drug, with treatment assignments designated according to actual study treatment received will be the primary population for evaluating safety and treatment compliance and administration.

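### Section 5.5 credits unreturned tablets as taken by default, so intervals with no return count get full credit and overall compliance is biased upward, possibly above 100%

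*Combined protocol and SAP*

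**What the plan says.** Section 5.5 (Measures of Treatment Compliance) states that "overall treatment compliance will be defined as the total dose in mg taken during the study divided by the expected total dose in mg". It then sets the default for drug that does not come back: "Tablets that are not returned will be considered to have been taken, unless otherwise specified in the case report form (CRF"). Patients are asked to bring back leftover drug and containers at clinic visits. The section does not say whether expected dose means 240 mg/day throughout or the dose prescribed after a reduction or hold. It has no category for an unknown count and no rule for ratios above 100%.

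The supply and dosing facts are elsewhere. Section 5.3.2: "The apalutamide 60-mg tablets will be packaged in 120-count" bottles. Section 5.3.3: "at a dose of 240 mg per day (4 x 60-mg tablets"). Section 5.3.4: "a treatment cycle will consist of 4 weeks (28 days"). Table 1 in Section 5.3.5 allows reduction to 3 and then 2 tablets a day. Section 10 ends treatment after 13 cycles. Sections 8.2 and 8.3 call for drug to be dispensed but give no quantity.

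Section 12.1 gives the use of the measure: the safety population "will be the primary population for evaluating safety and treatment compliance and administration".

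**The concern.** Tablets dispensed minus tablets returned is an upper limit on tablets swallowed. The two agree only when every unreturned tablet was taken. Section 5.5 makes that the default, so a patient with no return data receives the most favourable score available. A patient who took every dose and handed back the spare tablets can score lower than one who skipped doses and handed back nothing.

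What is at stake is the description of exposure to apalutamide, the drug given in both arms. If return rates differ between arms or sites, the compliance summary will partly reflect how well drug was collected. Under-dosing in uncounted intervals cannot be seen, and values above 100% could enter the table with no instruction on how to read them.

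**Working it through.** The documents state no compliance percentage or threshold, so there is no figure of the plan's own to reproduce.

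**Inputs**
- Bottle: 120 tablets of 60 mg (5.3.2).
- Tablets per day: 4 at full dose (5.3.3); 3 or 2 after reductions (Table 1).
- Cycle: 28 days (5.3.4); 13 cycles (Section 10).
- Assumption: one full bottle dispensed per 28-day cycle, at every dose level. Two bottles per two-cycle interval give the same ratios.

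**Formula.** Compliance = (dispensed − returned) × 60 mg ÷ expected mg. With expected dose in tablets, the 60 mg cancels.

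**1. Full dose, nothing returned in 13 cycles**
- Dispensed: 13 × 120 = 1560. Expected: 13 × 28 × 4 = 1456.
- Score: 1560/1456 = 107.1%.
- A patient who really took 84 of 112 tablets each cycle took 13 × 84 = 1092, or 1092/1456 = 75.0%. The score is still 107.1%, about 32 points too high.
- A patient who took everything and returned the 8 spare tablets each cycle scores (1560 − 13 × 8)/1456 = 100.0%.

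**2. One uncounted cycle, the other 12 perfect and counted**
- Score: (12 × 112 + 120)/1456 = 1464/1456 = 100.5%.
- If nothing was taken in that cycle, the truth is 1344/1456 = 92.3%.
- Each uncounted full-dose cycle can therefore add up to 120/1456 = 8.2 points.

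**3. Dose reductions, nothing returned, expected dose following the prescribed dose**
- 6 cycles at 240 mg and 7 at 120 mg: expected 6 × 112 + 7 × 56 = 1064; 1560/1064 = 146.6%.
- 1 cycle at 240 mg, 1 at 180 mg, 11 at 120 mg: expected 112 + 84 + 616 = 812; 1560/812 = 192.1%.

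**4. Same patients, expected dose held at 240 mg/day**
- 1560/1456 = 107.1% in every case.
- Under this reading a patient who takes a prescribed 120 mg/day perfectly and returns the rest scores 56/112 = 50% for that cycle. The undefined denominator therefore matters even when returns are complete.

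**5. Sensitivity to the assumptions**
- Visits carry a window of 7 days either way. One unreturned bottle over a 35-day full-dose interval scores 120/140 = 85.7%. The score is then below 100%, but 120 tablets are still credited whether or not they were taken.
- If the 4-tablet daily maximum in Section 5.5 is read as a limit on credited intake, an uncounted full-dose cycle scores 112/112 = 100%, again whatever was taken.

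**The case against.** The rule has an exception: a site can record on the CRF that tablets were lost or not taken. Section 5.4 also requires a per-patient log of tablets dispensed and returned, checked by the study monitor, and Sections 8.3 and 8.4 and Appendix 1 schedule compliance assessments. This stands in part. The exception means the bias is a default and not inevitable. But Section 5.5 gives no criteria for using it, and the log shows what came back, not what happened to tablets that did not.

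Several stronger readings are tempting and are not supported:
- **A range of 107% to 214% as fact.** The figure 120/56 = 214.3% is a single-cycle value at 120 mg/day. Section 5.5 defines a whole-study ratio, and every patient starts at 240 mg, so under the one-bottle assumption that ratio cannot reach 214%. The 107% itself depends on a dispensing quantity that the documents do not give.
- **Telemedicine removes drug return.** Section 7.1.3 says "All physical exams may be performed over a telemedicine visit", and Appendix 1 adds self-reported vital signs. Neither waives drug return or compliance assessment. What can be said is that no remote count or return step is described.
- **The rule hides grounds for stopping or changes who is evaluable.** Sections 4.3 and 10 list non-compliance with the protocol or study procedures as a reason to stop, but neither refers to this percentage or any threshold. Evaluability in Section 12.2.1 turns on discontinuation, withdrawal and loss to follow-up.
- **Patients with no counts are the least adherent.** The documents contain nothing on this.

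It is also fair to say that Section 12.2 specifies no compliance model or per-protocol set, so no inferential result moves.

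**Conclusion.** The concern holds in a limited form. By default, Section 5.5 turns missing return data into full intake, so the credited dose can err only upward wherever the CRF exception is not used. Assuming one 120-count bottle per 28-day cycle and no returns, overall compliance at full dose is 107% regardless of actual intake. It rises to about 192% in an extreme early-reduction case if expected dose follows the prescribed dose, and stays at 107% if it does not. With only one uncounted full-dose cycle in 13, the possible overstatement is about 8 points. How often counts will be missing cannot be known from the documents.

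The damage is confined to the descriptive compliance and exposure summary in the safety population. The primary comparison and its evaluability rule do not use this measure.

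**What to change.** Revise Section 5.5 as follows:

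1. Define expected total dose as the dose prescribed over each dispensing interval, allowing for reductions and holds.
2. Where no container is returned and no count is recorded for an interval, treat intake in that interval as unknown, not as taken. Keep the CRF entry as the place to record tablets known to be lost or not taken.
3. Report by arm the share of intervals with no count, and give overall compliance twice: a lower bound with uncounted tablets not taken, and an upper bound with all prescribed tablets taken.
4. Do not cap counted intake. A cap could hide real over-consumption, and overdose is a special reporting situation in Section 9.1.8. Flag values above 100% for query.

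In the one-uncounted-cycle example, the report would give 92.3% (1344/1456) to 100% (1456/1456) in place of a single 100.5%.

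The cost is one paragraph and a small programming change, using the log that Section 5.4 already requires. Some intervals become missing, and reported compliance may be slightly lower. Treatment, sample size and the primary analysis do not change.

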5.6 STEREOTACTIC BODY RADIATION

SBRT must be initiated within 90 days following initiation of apalutamide therapy for patients randomized to this treatment arm.

For the purposes of planning an SBRT treatment, CT- and/or MRI-simulation will be performed with fabrication of a radiation therapy immobilization device (such as a vacuum lock bag) which will be custom made for each patient. For tumors located in the upper abdomen or thorax, respiratory motion will be considered with methods including four-dimensional CT study or respiratory control to improve tumor targeting accuracy for those tumors that may be subject to respiratory motion.

The treating radiation oncologist will identify the location of the tumor. Gross tumor volume (GTV) delineation will be performed on sequential axial computed tomography images. An SBRT treatment plan will be developed based on tumor geometry and location. The clinical tumor volume (CTV) will typically equal the GTV or ITV (internal target volume). The dose will be prescribed to the minimal isodose line that completely covers the planning target volume (PTV) PTV (=CTV plus a 5 mm margin), except in cases where dose constraints to neighboring organs necessitates under dosage of the PTV. Adjacent normal structures including but not limited to the heart, esophagus, aorta, spinal cord, kidneys, rectum, bowel, liver, and stomach within 5 cm of the CTV will be identified for the purpose of limiting incidental radiation to these structures.

SBRT will be delivered in 1 to 5 fractions, and the dose and fractionation schedule will depend on the size and location of the lesion(s)/radiation field and the surrounding normal tissue constraints in accordance with AAPM Task Group 101 recommendations. Typical doses include 16 – 24 Gy in 1 fraction, 30 – 60 Gy in 3 fractions, and 30 – 60 Gy in 5 fractions. For example, while isolated osseous lesions may be treated in a single fraction (depending on location), lesions in the lung and liver will be treated in 3 to 5 fractions depending on their size (5 fractions for ≥ 3 cm) or location (central tumors in close proximity to the mediastinum).

Within three weeks of the initial treatment planning imaging study, SBRT will be administered using image-guidance. A vacuum lock bag (or equivalent immobilization approach) will be used to minimize movement of the chest, spine, and abdomen during treatment. During treatment, real time cone beam CT images of the patient's body site of interest will be obtained. Cone beam CT scan will be obtained immediately prior to treatment and will be repeated until the treatment shift, required to align the CT planning scan and the cone beam CT scan performed on the day of treatment cone beam CT, is within tolerance for the body site.

Equivocal lesions/radiation fields on PSMA PET scan that are not definitive for metastasis will not count towards the limit of 5 radiation fields and will not undergo SBRT. Patients will be evaluated for adverse events/toxicities during their treatment.

6 CONCURRENT MEDICATIONS

All patients should be maintained on the same medications throughout the entire study period, as medically feasible, with minimum introduction of new chronic therapies. Every medication or treatment taken by the patient during the trial and the reason for its administration must be recorded on the CRF. Standard medical treatment as applicable is allowed except for treatments noted in the eligibility criteria and/or listed in the prohibited medications section below.

Continuous treatment with a LHRH analogue or surgical castration is mandatory for all patients in order to maintain castrate concentrations of testosterone (<50 ng/dL). The choice of LHRH analogue is at the discretion of the investigator. Dose and dose schedule (without interruption) will be consistent with the prescribing information and should only be adjusted if clinically indicated to maintain castrate concentrations of testosterone. Maintenance of castrate level of testosterone is mandatory during both the On-Treatment and Post-Treatment periods of the study.

All patients should receive oral calcium and vitamin D supplementation while receiving apalutamide. For patients at high estimated fracture risk based on baseline DXA bone density scan (> 3% estimated 10 year risk of hip fracture or > 20% major osteoporotic fracture per FRAX calculator (<https://www.sheffield.ac.uk/FRAX/>), treatment with a bone-modifying agent (e.g. alendronate) should be administered as per institutional guidelines.

6.1 PROHIBITED MEDICATIONS AND TREATMENTS

As a class effect, androgen receptor antagonists have been associated with seizures due to an off-target mechanism of action (GABA_A inhibition). Patients will be closely monitored for seizures, but as a precautionary measure, drugs known to decrease the seizure threshold and/or cause seizure will be prohibited while on study. A list of these medications can be found in [Appendix 5](#).

6.2 RESTRICTED THERAPIES

Investigators should refer to the apalutamide Investigator's Brochure (Sections 4.3.3.3 and 5.10) and associated addenda for complete details on the drug interaction potential of apalutamide. Highlights of drug interaction are summarized below.

- Strong CYP3A4 inducers: the potential for drug-drug interactions with apalutamide has not been tested clinically. Strong inducers of CYP3A4 (eg, phenytoin, carbamazepine, rifampin, rifabutin, rifapentine, phenobarbital, efavirenz, tipranavir, St. John's wort) should be avoided as much as possible. Additional information is provided in [Appendix 5](#).
- Apalutamide may also induce CYP3A4; therefore, caution should be taken when administered in conjunction with CYP3A4 substrates that have a narrow therapeutic index.
- Strong CYP2C8 inhibitors (eg, gemfibrozil) should be used with caution with apalutamide.
- The potential for drug-drug interaction between apalutamide and warfarin (e.g., Coumadin) is unknown at present. If a patient is taking warfarin, re-assess (prothrombin) PT/(international normalized ratio) INR as clinically indicated and adjust the dose of warfarin accordingly.
- Corticosteroids (Oral, IV, or IM): due to possible resistance mechanisms, which may be contributed by glucocorticoid receptor signaling, concurrent use of corticosteroids during the study should be avoided whenever possible. Short term use of steroids (\leq 4 weeks) will be allowed if clinically indicated, however, its use must be tapered off as soon as possible.

6.3 LIFESTYLE GUIDELINES

To avoid risk of drug exposure through the ejaculate (even men with vasectomies), patients must use a condom during sexual activity while on study drug and for 3 months following the last dose of study drug. Donation of sperm is not allowed during the study and for 3 months following the last dose of study drug.

There are no data on the use of apalutamide in pregnancy. Maternal use of an anti-androgen is expected to produce changes in hormone levels that may affect fetal development. It is not known if apalutamide or its metabolites are present in semen.

If the patient is engaged in sexual activity with a woman of childbearing potential, a condom is required along with another effective contraceptive method consistent with local regulations regarding the use of birth control methods for patients participating in clinical studies and their partners. Highly effective forms of contraception include:

- established use of oral, injected or implanted hormonal methods of contraception; placement of an intrauterine device (IUD) or intrauterine (IUS) system;

- barrier methods: condom with spermicidal foam/gel/film/cream/suppository or occlusive cap (diaphragm or cervical/vault caps) with spermicidal foam/gel/film/cream/suppository;
- vasectomy;
- true abstinence (an option when this is in line with the preferred and usual lifestyle of the patient).

Two highly effective forms of contraception are required during the study and for 3 months after the last dose of study drug.

7 STUDY PROCEDURES AND GUIDELINES

A Schedule of Activities representing the required testing procedures to be performed during the study is diagrammed in [Appendix 1](#).

Prior to conducting any study-related activities, written informed consent and any other authorizations must be signed and dated by the patient or patient's legal representative.

7.1 CLINICAL ASSESSMENTS

7.1.1 Demographics

Demographic information (e.g., date of birth, race) will be recorded at Screening.

7.1.2 Medical History

Relevant medical history, including history of current disease, other pertinent clinical conditions, and information regarding underlying diseases will be recorded at Screening.

7.1.3 Physical Examination

A complete physical examination will be performed by either the Investigator or a sub-Investigator at Screening. Qualified staff (e.g., nurse practitioner or physician assistant) may complete either a full or abbreviated physical exam at all other visits. New abnormal physical exam findings must be documented and followed by a physician or other qualified staff at the next scheduled visit. All physical exams may be performed over a telemedicine visit.

7.1.4 Vital Signs

Heart rate and blood pressure will be recorded after resting for 5 minutes at Screening and every scheduled visit during treatment and at the end of treatment. If the physical exam is a telemedicine visit, BP and heart rate will be self-reported by the patient.

7.1.5 Performance Status

The Eastern Cooperative Oncology Group (ECOG) performance status scale will be used ([Appendix 3](#)) and will be assessed at Screening and every subsequent clinic visit.

7.1.6 Adverse Events

Assessment of adverse events will include type, incidence, severity (graded by the National Cancer Institute [NCI] Common Terminology Criteria for Adverse Events [CTCAE], Version 4.03), timing, seriousness, and relatedness ([Appendix 4](#)). Adverse events will be assessed at every clinic visit.

7.1.7 Concomitant Medications/Therapies

All concomitant medication and concurrent therapies will be documented from screening until 30 days after the last dose of study drug. Name, indication for administration, and dates of medication or therapy will be captured.

7.1.8 Tumor Assessments

Whole body PSMA-PET imaging will be performed within 42 days of randomization during the Screening period. PSMA PET imaging may use Ga-PSMA-11 or other PSMA PET tracer. Either PSMA PET/MR or PET/CT is allowed. A certified trained nuclear medicine physician will evaluate the baseline PSMA-PET scan for purposes of eligibility determination to verify whether there are ≥ 1 but ≤ 5 discrete radiation fields. A treating radiation oncologist will review baseline scans to determine whether the lesion(s) identified on baseline PSMA PET scan are amenable to SBRT.

If more than 5 radiation fields are identified on baseline PSMA PET scan the patient will be deemed Screen Failure and will be treated per investigator discretion.

Patients will undergo optional follow up PSMA PET scan at the time of PSA progression by PCWG criteria. PSA progression will be defined as an increase of at least 2 ng/mL and 25% above the nadir or baseline on study, whichever is lower, confirmed by repeat PSA measurement at least 2 weeks later.

7.1.9 Tumor Biopsy (DISCONTINUED)

An optional biopsy and biomarker blood collection was to be conducted under the PROMOTE study (CC155518, IRB# 15-18365), as an optional enrollment option. The PROMOTE study has closed to accrual and will no longer be able to financially support the biopsy, biomarker collection, and downstream correlates. Therefore, we are discontinuing the biopsy and biomarker blood collection moving forward described in the italicized paragraph below (as of Amendment 8.0). Any specimens collected under prior protocol versions (i.e., prior to implementation of Amendment 8.0) may continue to be stored and/or used as permitted according to the PROMOTE study protocol and ICF.

Patients will undergo optional baseline image-guided core needle tumor biopsy of PSMA-avid metastatic lesion if lesion is safely accessible. Lesions will be chosen based upon the strength of the evidence suggesting the presence of metastasis and with the goal of minimizing patient risk. Soft tissue lesions should be prioritized for biopsy. If the Radiologist in charge of the procedure cannot identify a lesion amenable for biopsy, the patient will still be treated on study.

Patients undergoing biopsy must have a PT or INR and a PTT ≤ 1.5 times the institutional ULN within 14 days prior to biopsy. Patients on warfarin, aspirin, or other anti-coagulants may undergo biopsy, provided they are deemed able to tolerate discontinuation of anti-coagulation for one week prior to the baseline biopsy. Conversion to low molecular weight heparin prior to biopsy is permitted per local standard operating procedures, provided there is agreement regarding the procedure between the treating physician, the interventional radiologist and the PI.

The biopsies will be performed in an interventional radiology suite with radiological guidance (typically CT or MRI) in accordance with the standard operating procedure according to institutional standards. Once the target lesion(s) identified, up to six (6) biopsies will be performed. Preferably, a 16 gauge Bonpty™ needle or biopsy needle with an equivalent 16g bore will be used to biopsy the metastatic lesion. If the lesion is a bone metastasis, the Bonpty needle will be passed through the cortical bone and into the target lesion. Optimal results are obtained when the biopsies are performed on medullary bone directly adjacent to blastic lesion. Soft tissue biopsies should be taken so that a core of approximately 10 to

20 mm in length is obtained. Core biopsies will be extracted: up to 3 will be placed in neutral-buffered formalin and up to 3 will be immediately frozen on a pre-frozen bed of OCT (Optimal Cutting Temperature compound used for frozen sections), covered with additional OCT, and kept on dry ice or at -80° C.

